## **Introduction**

### **1.1 Purpose of the Statistical Analysis Plan (SAP)**

This statistical analysis plan has been developed to (1) provide a structured time-frame for database completion and preparation of the final primary analysis report; (2) facilitate discussion of the key statistical analysis components amongst the study team; (3) provide agreement between the study team and statisticians regarding the statistical analyses to be performed; and (4) aid in setting priorities relating to the data cleaning and development of statistical analysis programs.

The statistical analysis plan contains details of all statistical analyses that will be completed for the final primary analysis report.

### **1.2 Study Design (Protocol Version 2.0)**

This study is a randomized, double-blind, placebo-controlled non-inferiority trial designed to assess the overall safety and toxicity of 28 weeks of isoniazid (INH) preventive therapy (IPT) initiated during pregnancy versus deferred initiation of IPT at 12 weeks postpartum in HIV-infected pregnant women and their infants at high risk for TB infection and disease. The study will also assess the efficacy of these strategies in the women and their infants, safety and toxicity of INH *in utero* and on infants, INH resistance among *Mycobacterium tuberculosis* (*M.tb.*) isolates among participants who develop TB while on study, intensive PK of INH and ARV drugs among HIV-infected women on HAART, adherence to INH during pregnancy and postpartum, and performance characteristics of IGRA with TST among HIV-infected pregnant women and their infants.

A target of 950 HIV-infected pregnant women at  $\geq 14$  to  $\leq 34$  weeks (34 weeks, 6 days) of gestation and living in high TB incidence areas, defined as having 60 TB cases per 100,000 population in the WHO TB annual report, will be enrolled. Women who are suspected of having TB with a positive WHO TB symptom screen, have reported recent exposure to an active TB case, have received INH or TB treatment for  $>30$  days in the past year, have evidence of acute hepatitis within 90 days prior to study entry, or have  $\geq$ Grade 1 peripheral neuropathy will not be eligible.

Participants will be stratified based on gestational age at entry, and will be randomized in equal proportions to one of the following two groups:

- ARM A: Maternal INH at study entry for 28 weeks and then switched to placebo for INH until 40 weeks postpartum (immediate IPT), or
- ARM B: Maternal placebo for INH from study entry until 12 weeks postpartum and then switched to INH for 28 weeks until 40 weeks postpartum (deferred IPT)

Each maternal participant will also receive vitamin B6 and multivitamins from study entry until 40 weeks postpartum, as well as intensified TB case finding, and will be followed up to 48 weeks postpartum. Each infant participant will be followed from birth until 48 weeks postpartum with

intensified TB case finding.

The primary hypothesis is that initiation of IPT during pregnancy among HIV-infected pregnant women is as safe as deferring IPT to 12 weeks postpartum.

## **2 Study Objectives (Protocol Version 2.0)**

The primary analysis report will include the primary objective and secondary objectives 1-4 (listed in sections 2.1 and 2.2 below). Secondary objectives 5-7 and the exploratory objectives (section 2.3) will be addressed in separate analysis plans.

### **2.1 Primary Objective**

To compare overall safety and toxicity of immediate versus deferred INH preventive therapy in HIV-infected pregnant women enrolled at  $\geq 14$  through  $\leq 34$  weeks gestation (34 weeks, 6 days)

### **2.2 Secondary Objectives**

1. To compare safety and toxicity of INH *in utero* exposure and on infants on study
2. To compare TB incidence and all-cause mortality in HIV-infected women and their infants enrolled on study
3. To compare overall safety and hepatotoxicity, as well as evaluate risk factors for these outcomes, during pregnancy and immediate postpartum in women on immediate versus deferred INH therapy
4. To evaluate for INH resistance among *M.tb.* isolates from HIV-infected women and infants who develop TB while on study
5. To evaluate the intensive pharmacokinetics of INH and selected ARV drugs in a subset of HIV-infected pregnant and postpartum women receiving HAART
6. To evaluate and compare the performance characteristics of IGRA (TB ELISPOT and QGIT) with TST in HIV-infected women and their infants
7. To compare adherence in women initiating immediate versus deferred INH preventive therapy via self-report and pill counts

### **2.3 Exploratory Objectives**

1. To evaluate population pharmacokinetics and pharmacogenomics of INH and EFV in HIV-infected pregnant and postpartum women
2. To assess the effects of INH preventive therapy on the functional characteristics of TB specific T-cell responses measured by TB ELISPOT in HIV-infected women and their infants on study
3. To evaluate adherence and exposure to INH and EFV using drug levels in hair and analyze the association between these drug levels and adverse events
4. To compare the two arms with respect to the overall (risk:benefit) clinical outcome of the mother-infant pairs
5. To explore associations of maternal and infant specific TB responses and novel biomarkers with risk of maternal and infant TB infection and disease

6. To explore the neurotoxicity of INH in combination with EFV in a subset of women

A brief description of the important study time points is shown in the following table:

Evaluations	Time points of interest
Adverse events in mothers (for primary safety analysis)	Up to week 48 postpartum
Adverse events in infants	Up to week 48 from birth
Adverse pregnancy outcomes	Delivery to week 48 from birth
Maternal TB	Up to week 48 postpartum
Infant TB	Up to week 48 from birth
Intensive and sparse PK in mothers	Antepartum (third trimester) and week 16 postpartum
TST in mothers	Delivery (or Week 4 postpartum if not done at delivery) and Week 44 postpartum
TST in infants	Week 44 from birth
IGRA in mothers	Entry, delivery and Week 44 postpartum
IGRA in infants	Week 44 from birth

### **3 Outcome Measures**

#### **3.1 Primary Endpoint**

Grade  $\geq 3$  AEs possibly, probably, or definitely associated with INH/Placebo for INH or permanent discontinuation of INH/Placebo for INH due to an adverse reaction in women after randomization until 48 weeks postpartum.

Study drug attribution is based on adjudication by an Independent Endpoint Review Committee (IERC), which consists of OB/GYN and pediatric specialists who are not members of the study team. Refer to the Endpoint Review Process document for details of the review process.

Adverse events include laboratory results, signs/symptoms, or diagnoses reported in the study database. Note that for hematology results, only those collected at delivery are considered in the primary endpoint since testing at other study visits specified in protocol Version 1.0 was discontinued in Version 2.0. Except for the following, diagnoses are based on Appendix 100 definitions and grading of adverse events is based on the DAIDS Table for Grading the Severity of Adult and Pediatric Adverse Events (Version 1.0, dated December 2004) grading criteria:

- As stated in Section 6.1.4 of the protocol, grading for ALT (SGPT), AST (SGOT) and total bilirubin (or direct bilirubin for women taking Atazanavir) are based on the modified grading table for hepatotoxicity in Appendix III of the protocol.
- As stated in Section 6.1.3 of the protocol, the Brief Peripheral Neuropathy Screen (BPNS) grading criteria (see Appendix II of protocol) will be used instead of the DAIDS grading criteria; signs/symptoms should be present for at least two weeks to be considered peripheral neuropathy.

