### **5.3.1 Demographics**

- Age (years): N, N missing, mean (s.d.), min, max, median (Q1-Q3); number (%) by age group (eg. <24, 24-<29, 29-<34,  $\geq$ 34) with years rounded down [STATUS]
- Self-reported race/ethnicity: number (%) by category [STATUS]
- Country: number (%) [STATUS]
- Gestational age (weeks) at entry: N, N missing, mean (s.d.), min, max, median (Q1-Q3); number (%) by category (14-<24, 24-34) [OBW0006]
  - Note: Gestational age is determined based on best available method, with methods prioritized as (i) ultrasound, (ii) last menstrual period, (iii) fundal height, and may

not match the level used for stratification if the site defined best available method differently.

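### Haematology labs count toward the 48-week primary endpoint only at delivery, so those from the deferred arm's INH course cannot count; one sensitivity row would show whether this matters

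*SAP*

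**What the plan says.** Section 3.1 defines the primary endpoint over the period "in women after randomization until 48 weeks postpartum". It takes in several kinds of event: "Adverse events include laboratory results, signs/symptoms, or diagnoses reported in the study database". Permanent discontinuation of blinded study drug for an adverse reaction also counts. Haematology labs are then restricted: "only those collected at delivery are considered in the primary endpoint". The reason given is operational, namely that "testing at other study visits specified in protocol Version 1.0 was discontinued in Version 2.0".

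Section 1.2 sets the exposure periods. Immediate arm: "Maternal INH at study entry for 28 weeks and then switched to placebo for INH until 40 weeks postpartum". Deferred arm: "Maternal placebo for INH from study entry until 12 weeks postpartum and then switched to INH for 28 weeks until 40 weeks postpartum". Entry is from 14 weeks to 34 weeks 6 days of gestation, and section 5.3.1 tabulates entry gestational age as "number (%) by category (14-<24, 24-34" weeks.

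Section 4.1 compares the arms by 48 weeks postpartum. Non-inferiority is shown if the upper confidence bound for the difference is below 5%.

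**The concern.** The delivery-only rule reads the same for both arms, but the single countable sample falls in different treatment phases. In the immediate arm it falls during INH. In the deferred arm it falls before INH starts. A 48-week window is long enough to contain both INH courses, yet the haematology-lab component compares INH with placebo at one time point.

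At stake is how a failed or borderline non-inferiority result would be read. Part of an observed difference could reflect when blood was drawn, not how toxic the two schedules are. No planned analysis separates this out:

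- The per-protocol, as-treated, death-coding and simple-proportion analyses in section 4.1.1 state no different rule for haematology.
- The all-cause Grade 3 or higher analysis is meant to check for bias, but it drops attribution and does not address sampling time. The SAP does not say whether the delivery-only rule applies there.
- The section 5.9 table of most severe outcome splits by grade and type of outcome, not by the lab that made a woman qualify.

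**Working it through.** **Timing (inputs from sections 1.2 and 3.1).**

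- Immediate arm, earliest entry: 14 + 28 = 42 weeks of gestation at the end of INH.
- Immediate arm, latest entry: 34 weeks 6 days + 28 weeks = 62 weeks 6 days of gestation-equivalent.
- At a 40-week delivery, time since starting INH runs from 40 weeks − 34 weeks 6 days, about 5 weeks, to 40 − 14 = 26 weeks. Both are below 28. The exception is delivery after 42 weeks in a woman who entered at the very start of the window.
- Deferred arm: INH starts 12 weeks after delivery and ends at 12 + 28 = 40 weeks postpartum. The delivery sample always precedes it.
- Countable haematology samples during assigned INH: one in the immediate arm, none in the deferred arm.

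**Direction.** Let each INH course produce attributed Grade 3 or higher haematology results in a share *h* of women, over and above what is attributed to blinded placebo. Assume *h* is equal in both arms and does not overlap with other endpoints. The true difference is then 0. The observed immediate-minus-deferred difference is between 0 and +*h*, and reaches +*h* only if the one delivery sample captures the whole excess.

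**Illustrative size.** The SAP gives a target of 950 randomised equally, so 950 / 2 = 475 per arm, and a 5-point margin. It gives no event rate, no power and no haematology rate, so there is no stated figure to reproduce. Assumptions: base rate *p* of 5% or 10%; *h* of 0.5%, 1% or 2%; full capture at delivery; a two-sided 95% interval (section 4.1 gives the 5% level but not the sidedness); unpooled normal approximation for proportions; no loss to follow-up.

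- Delivery-only: SE = √{[(*p*+*h*)(1−*p*−*h*) + *p*(1−*p*)] / 475}; power = Φ((0.05 − *h*)/SE − 1.96).
- Both courses sampled alike: SE = √{2(*p*+*h*)(1−*p*−*h*) / 475}; power = Φ(0.05/SE − 1.96).

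Worked case, *p* = 5%, *h* = 1%:

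- Delivery-only: SE = √[(0.0564 + 0.0475)/475] = 0.01479; 0.04/0.01479 − 1.96 = 0.745; power 77.2%.
- Sampled alike: SE = √[2 × 0.0564/475] = 0.01541; 0.05/0.01541 − 1.96 = 1.285; power 90.1%.

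| Base rate *p* | Excess *h* | *h* as share of margin | Power, delivery-only | Power, sampled alike |
|---|---|---|---|---|
| 5% | 0.5% | 10% | 87.5% | 92.2% |
| 5% | 1% | 20% | 77.2% | 90.1% |
| 5% | 2% | 40% | 49.5% | 85.5% |
| 10% | 0.5% | 10% | 62.8% | 71.0% |
| 10% | 1% | 20% | 52.0% | 69.2% |
| 10% | 2% | 40% | 31.5% | 66.0% |

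The delivery-only column is a worst case. If the delivery sample captured half of the excess, the shift would be *h*/2. At the 10% base rate the same formula then gives 68.0%, 62.8% and 52.0% for *h* = 0.5%, 1% and 2%.

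**The case against.** The strongest reply is that the plan did not choose this freely. Routine haematology at other visits stopped with protocol Version 2.0, and the SAP cannot count results that were not collected. That stands. The point concerns how the consequence is reported, not the restriction itself.

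Much of the raw information is also planned already. Section 5.14 lists by arm each woman with a primary endpoint, with the event, its grade and its week. Section 5.4 tabulates Grade 3 or 4 primary adverse events by MedDRA code. Section 5.9 estimates the difference up to delivery and up to 12 weeks postpartum. This also stands and lowers the importance of the point. What remains missing is a re-estimate of the 48-week difference without the delivery labs.

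A reader might draw stronger conclusions that the SAP does not support:

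- *Every INH-attributed haematology result widens the difference.* No. The endpoint counts events attributed to INH or to its placebo, under blinding, so deferred-arm delivery results attributed to study drug offset. Only an excess over placebo shifts the difference, and the SAP gives no evidence that one exists.
- *No haematological event in the deferred INH course can count.* This is true of lab results only. The other routes in section 3.1 stay open to 48 weeks.
- *The shift equals the incidence per INH course.* One sample captures at most that.
- *Non-inferiority could be claimed falsely.* The mechanism raises the immediate-minus-deferred difference, which makes the claim harder to reach.

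**Conclusion.** The asymmetry is real and follows directly from sections 1.2 and 3.1. It is confined to haematology labs in the 48-week comparison. In the analyses up to delivery and up to 12 weeks postpartum, the deferred arm has not yet started INH, so INH against placebo is the intended contrast.

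For schedules of equal toxicity the distortion runs from zero up to the excess of attributed Grade 3 or higher haematology results on INH over placebo. It is conservative for the non-inferiority claim. A positive result is not undermined by it; a failure or near-miss would be harder to interpret.

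The size is unknown, and every power figure rests on assumed rates and full capture at delivery. Over the range shown, the loss against equal sampling goes from 92.2 − 87.5 = 4.7 points (5% base rate, 0.5% excess) to 85.5 − 49.5 = 36.0 points (5% base rate, 2% excess). With no excess there is no loss. Severity: minor, optional.

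**What to change.** Add one sensitivity analysis to section 4.1.1 and one row to the section 5.9 output: the stratified 48-week difference in the primary endpoint, with delivery haematology labs not counted as qualifying events. Women who qualify only through such a lab stay in the analysis and are recoded as not having the endpoint on that basis; they are not dropped. A woman with another qualifying event, including permanent discontinuation for an adverse reaction, keeps the endpoint through that event. Report the number of women affected in each arm beside the primary result.

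The cost is one more run of the existing program and one table row. No new data are needed, since the section 5.14 listing already carries the qualifying event by arm. The downside is that the sensitivity estimate leaves out haematology labs altogether, so it removes the unequal sampling but does not compare haematological toxicity between the two INH courses.

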### **3.2 Secondary Endpoints**

- ***In utero* exposure and infant endpoints:**
  - Fetal death
  - Small for gestational age
  - Premature birth (< 37 weeks gestation)
  - Low birth weight (< 2500 gm)
  - Congenital anomalies
  - Grade 3 or higher clinical or laboratory AEs
    - ◆ all AEs
    - ◆ possibly, probably, or definitely related to INH/Placebo for INH
  - HIV infection
  - Hospitalization
- **Any of the following endpoints:**
  - Maternal TB (probable or confirmed – see Appendix 100 for definitions)
  - Infant TB (probable or confirmed, as defined in Appendix 100, and congenital TB, as defined using the Cantwell criteria)
  - Death of infant
  - Death of mother
  - Combined endpoint of maternal TB or maternal death
  - Combined endpoint of infant TB or infant death
  - Combined endpoint of maternal TB, maternal death, infant TB, or infant death

NOTE: TB endpoints and infant cause of death will be reviewed by a Secondary Endpoint Review Committee (SERC), which consists of maternal and pediatric TB specialists who may be

members of the study team. Refer to the Endpoint Review Process document for details of the review process. Appendix 100 will be the basis for adjudication of the TB endpoint by the SERC and is available in the CRF Appendix Codes section of the Frontier Science IMPAACT Portal; the web link to portal can be found in the MOP. Cantwell criteria for Congenital TB are in the MOP and will be collected on the P1078 CRF.

Deaths of enrolled women will receive external review by the IERC for adjudication of study treatment attribution and will also be reviewed by the SERC. The SERC will consider if the cause of death (COD) is due to unrecognized active TB (expected to be rare), from a known cause other than active TB, or from an unknown cause.

- **Occurrence of each of the following safety outcomes in HIV-infected women: during pregnancy up to: (i) delivery (antenpartum) and (ii) 12 weeks postpartum**
  - Grade  $\geq$  3 AEs possibly, probably, or definitely related to INH/Placebo for INH or permanent discontinuation of INH/Placebo for INH due to an adverse event
  - Grade  $\geq$  3 AEs (all-cause)
  - Hepatotoxicity possibly, probably, or definitely related to INH/Placebo for INH
  - Hepatotoxicity (all-cause)

Note: Each of the definitions of hepatotoxicity will be studied: (i) having  $\geq$  Grade 3 LFTs (ALT  $> 5 \times$  ULN or ALT  $> 3 \times$  ULN with bilirubin  $> 2 \times$  ULN) or ALT  $> 3 \times$  ULN with persistent, symptomatic clinical hepatitis); and (ii) using DAIDS AE grading criteria, Version 1.0.

- **Resistance outcomes:**
  - Resistance to INH in isolates of *M.tb* from mothers who develop culture-confirmed TB
  - Resistance to INH in isolates of *M.tb* from infants who develop culture-confirmed TB

### 3.3 Other Outcomes

- **Latent TB Diagnostic Outcome Measures**
  - IGRA assay result (positive, negative, indeterminate) in women
  - IGRA assay result (positive, negative, indeterminate) in infants
  - TST result (positive or negative) in women; TST positive if  $\geq 5$  mm
  - TST result (positive or negative) in infants; TST positive if  $\geq 10$  mm in HIV-negative infants and if  $\geq 5$  mm in HIV-positive infants
- **Adherence to INH/Placebo for INH among women, assessed by self-report and pill count**
  - For the self-report and pill counts, adherence will be considered as a continuous, ordinal categorical, or a binary variable. When presented as a continuous variable, adherence is defined as the percentage of expected doses/pills taken during the entire treatment period (28 weeks). When presented as an ordinal variable, excellent adherence is defined as taking at least 90% of doses/pills

during the entire treatment period; good adherence as  $\geq 80\%$  to  $< 90\%$ ; reasonable adherence as  $\geq 60\%$  to  $< 80\%$ ; and poor adherence as  $< 60\%$  of doses, as reported in any of the scheduled adherence evaluations. When presented as a binary variable (completer versus non-completer), a completer is defined as having excellent adherence.

- **Population Pharmacokinetics**
  - Primary: Area under the plasma versus time curve (AUC) at each of two time points (antenpartum and postpartum) in women.
  - Secondary:  $C_{\text{peak}}$ , half-life ( $t_{1/2}$ ), volume of distribution ( $V_d$ ) and apparent clearance (CL/F)
- **Pharmacogenetics**
  - Presence of genetic variants to NAT2 and 2E1, PK of INH and EFV based on sparse sampling during pregnancy and postpartum
- **Immunologic Outcome Measures**
  - Functional and phenotypic characteristics of TB specific T-cell responses in women
  - Functional characteristics of TB specific T-cell responses in infants
- **Drug Levels in Hair**
  - INH and EFV drugs levels in women's hair samples; adverse events are as defined Grade 3 or higher adverse events in women until 48 weeks postpartum
- **Risk-benefit Outcome**
  - An overall ordinal measure of clinical outcomes in the mother-infant pair, which assigns a score to the mother-infant pair according to severity of totality of clinical outcomes (clinical outcomes include maternal death, maternal TB, maternal safety events, infant death, infant TB, infant safety events); the measure will be formulated in consultation with the study team prior to release of final analysis results to the team, and details will be included in the statistical analysis plan (SAP) for this secondary analysis.
- **Maternal and infant specific TB responses and novel biomarkers**
  - Anti-mycobacterial antibody responses in maternal plasma at all weeks when samples are collected
  - Anti-mycobacterial antibody responses in infant plasma at all weeks when samples are collected
  - Inflammation and immune activation markers (and other potential biomarkers) measured from maternal plasma/PBMC samples at all available time points
  - Inflammation and immune activation markers (and other potential biomarkers) measured from infant plasma/PBMC samples at all available time points

- **Neurotoxicity**
  - Depression scores determined from the PHQ-9 instrument; responses to neurocognitive impairment questions and Pittsburgh Sleep Quality Index subset questions

## **4 Statistical Methods**

### **4.1 Analysis of the Primary Objective**

Safety of INH will be assessed primarily by comparing rates of Grade  $\geq 3$  events possibly, probably or definitely associated with INH/Placebo for INH or permanent discontinuation of INH/Placebo for INH due to an adverse reaction between women in the immediate and deferred arms by 48 weeks postpartum.

For the final primary analysis, a confidence interval for the absolute difference in primary endpoint rates will be presented as study entry gestational age-stratified Mantel-Haenszel estimates with the confidence interval computed using the method of Greenland and Robins (Biometrics 1985;41:55-68), and will use the rounded value of 5% significance level given that sequential monitoring with a Haybittle-Peto use function boundary (alpha-value) was used for interim analyses. Non-inferiority of immediate IPT in HIV-infected pregnant women with regards to safety will be demonstrated if the upper bound of this confidence interval is less than 5%. Unweighted (i.e., ignoring stratification) estimates for the difference in rates will also be reported. (Note: Although HAART use at study entry was a stratification factor in Version 1.0 of the protocol, and removed as stratification factor in Version 2.0, analyses will not stratify by HAART use at study entry because all women enrolled - except one - were on HAART at study entry.)

Data will be censored at the latest clinic visit (or contact with the participant while) on study when the endpoint status was ascertained prior to or at the earliest of the following times: (1) date when lost to follow-up for any reason, (2) date of death due to reasons not related to INH/Placebo, (3) date of permanent discontinuation of INH/Placebo as TB preventive therapy for any reason (other than an adverse reaction) including initiation of open label TB preventive therapy or treatment of presumed active TB disease, (4) date of last observed clinic visit or communication with the participant (on or before week 48 postpartum visit window). Participants who were lost to follow-up had their last date of clinic visit (or site contact) while on study before the week 48 postpartum visit window.

The primary safety analysis will be intent-to-treat, with participants analyzed according to randomized study arm.

